13.2 EVALUATION OF DISEASE RESPONSE

Response determination will be defined based on RECIST 1.1. (Table 4,5,6).

Table 4. Definition of Response in Target Lesions.

Response	Definition
Complete Response (CR)	Disappearance of all target lesions
Partial Response (PR)	At least a 30% decrease in the sum of the diameters of target lesions, taking as reference the baseline sum diameters
Progressive Disease (PD)	At least a 20% increase in the sum of the diameters of target lesions compared to baseline sum of target lesions, or any new lesions
Stable Disease (SD)	Neither sufficient decrease to qualify as a PR or sufficient increase to qualify as PD

Per RECIST 1.1, response should be confirmed by a repeat CT scan. The scan for confirmation of response may be performed at the earliest 4 weeks after imaging that showed response (if clinically indicated) or at the next scheduled scan.

Lesions that can be measured clinically on physical exam (skin lesions or palpable lymph nodes) will be measured by the investigator with the longest axis recorded. These measurements can be used to guide clinical decision making, for example prompting an earlier CT scan to evaluate disease. However, only measurements based on radiology will be used to determine response.

Table 5. Assessment of Non-Target Lesions

Response	Definition
Complete Response (CR)	Disappearance of all non-target lesions
Incomplete Response/Stable Disease (SD)	Persistence of one or more non-target lesions
Progressive Disease	Appearance of one or more new lesions and/or unequivocal progression of existing non-target lesions

Although a clear progression of “non-target” lesions only is exceptional, in such circumstances, the opinion of the treating physician should prevail.

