5.0 INCLUSION/EXCLUSION CRITERIA

5.1 INCLUSION CRITERIA

1. Recurrent and/or Metastatic squamous cell carcinoma of the head and neck that is not amenable to therapy with curative intent. Patients who refuse salvage surgery or radiation for recurrence are eligible.
2. Failure of prior immunotherapy as defined as:
 - a. Progression of disease on anti-PD-1 mAb or anti-PD-L1 mAb treatment in the R/M setting.
 - b. Both patients that have received platinum based chemotherapy prior or have not yet received platinum based chemotherapy are eligible.
3. Patients cannot have received more than 3 total lines of prior systemic therapy in the recurrent/metastatic setting
4. ECOG performance status of 0-1
5. Have at least one measurable area of disease (Target Lesion) based on RECIST 1.1.
6. Provide adequate tissue (core or incisional/excisional biopsy) prior to starting study for analysis for gene expression of LAG3 and CTLA4 per OmniSeq Immune Report Card. FNA is not adequate. Archival tissue can only be used if it was obtained in the recurrent/metastatic setting and there has been no subsequent cancer treatment after that tissue was obtained.
7. Life expectancy of at least 12 weeks based on investigator estimate.
8. Age \geq 18 years old
9. LVEF assessment with documented LVEF \geq 50% by either TTE or MUGA (TTE preferred test) within 6 months from first study drug administration
10. Patients must have normal organ and marrow function as defined below:

– absolute neutrophil count	\geq 1,500/mcL
– platelets	\geq 100,000/mcL
– total bilirubin	\leq institutional upper limit of normal (ULN)
– AST(SGOT)/ALT(SGPT)	\leq 2.5 \times institutional ULN
– creatinine	\leq institutional ULN

OR

– glomerular filtration rate \geq 40 mL/min/1.73 m ² for patients with creatinine levels (GFR) above institutional normal.	
---	--
10. Female subjects of childbearing potential must have a negative urine or serum pregnancy test within 28 days prior to receiving the first dose of study medication. If the urine test is positive or cannot be confirmed as negative, a serum pregnancy test will be required. Pregnancy testing will be repeated on C1D1 prior to the first doses of study medication.

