13.0 ASSESSMENT OF DISEASE

13.1 DEFINITIONS

Measurable Lesions: Lesions that can be accurately measured in at least one dimension with longest diameter at least >10 mm on CT scan (or >20 mm by X-ray). Cystic lesions thought to represent cystic metastasis can be considered as measurable lesions.

Malignant Lymph Nodes: To be considered pathologically enlarged and measurable, a lymph node must be > 15 mm when assessed by CT scan.

Non-measurable Lesions: All other lesions < 10 mm or lymph nodes < 15 mm by CT scan.

Target Lesions: All measurable lesions up to a maximum of 2 lesions per organ and up to 5 lesions in total, representative of all involved organs, should be identified as target lesions and recorded and measured at baseline. Target lesions should be selected on the basis of their size (lesions with the longest diameter), be representative of all involved organs, but in addition should be those that lend themselves to reproducible repeated measurements. It may be the case that, on occasion, the largest lesion does not lend itself to reproducible measurement. In this circumstance, the next largest lesion which can be measured reproducibly should be selected. A sum of the diameters (longest for non-nodal lesions, short axis for nodal lesions) for all

target lesions will be calculated and reported as the baseline sum diameters. If lymph nodes are to be included in the sum, then only the short axis is added into the sum. The baseline sum diameters will be used as reference to further characterize any objective tumor regression in the measurable dimension of the disease.

Non-target Lesions: All other lesions (or sites of disease) including any measurable lesions over and above the 5 target lesions should be identified as non-target lesions and should also be recorded at baseline.

Measurements of these lesions are not required, but the presence, absence, or in rare cases unequivocal progression of each should be noted throughout follow-up.

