13.3 EVALUATION OF BEST OVERALL RESPONSE

The best overall response is the best response recorded from the start of the treatment until disease progression/recurrence.

Table 6. Best Overall Response

Target Lesions	Non-Target Lesions	New Lesions	Overall Response
CR	CR	No	CR
CR	PR/SD	No	PR
PR	Non-PD	No	PR
SD	Non-PD	No	SD
PD	Any	Yes or No	PD
Any	PD	Yes or No	PD
Any	Any	Yes	PD

Given the observed pattern of response with immunotherapy medications where some patients develop evidence of progressive disease by RECIST 1.1, with significant increase in size of target lesions and/or new lesions, followed by regression of disease to SD or PR/CR all imaging showing progressive disease by RECIST 1.1, in the absence of significant clinic deterioration of the patient will be confirmed with a repeat CT scan at least 4 weeks from the initial imaging showing progression. Clinically stable patients will continue treatment in the interim before this scan. If progressive disease is confirmed on subsequent imaging, the patient will be defined as having progressive disease and will be taken off of the study. Progressive disease by RECIST 1.1 with clinical deterioration by the patient will be counted as progressive disease, and study treatment will be discontinued.

Determination of clinical deterioration is at the discretion of the treating physician as defined by progression of disease at critical sites requiring urgent intervention (for example cord compression), or development of signs and symptoms of disease progression and/or significant decline in ECOG performance status.

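### Table 4 sets no millimetre minimum for target-lesion progression, so a 2 to 3 mm change in a single 10 to 15 mm lesion meets the criterion on that scan; the confirmatory CT reduces this risk but does not remove it

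*Combined protocol and SAP*

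**What the plan says.** Section 5.1, item 5 asks that a patient "Have at least one measurable area of disease (Target Lesion) based on RECIST 1.1". Section 13.1 treats a non-nodal lesion as measurable at "longest diameter at least >10 mm on CT scan"; for nodes, "a lymph node must be > 15 mm when assessed by CT scan". A patient can therefore enter with a baseline sum of little more than 10 mm.

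Section 13.2 states that "Response determination will be defined based on RECIST 1.1" and refers to Tables 4 to 6. Table 4 gives the target-lesion rule for progression: "At least a 20% increase in the sum of the diameters of target lesions compared to baseline sum of target lesions"; any new lesion also counts. No absolute minimum appears in sections 13.1 to 13.3.

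Section 13.3 adds a safeguard. Without significant clinical deterioration, imaging progression "will be confirmed with a repeat CT scan at least 4 weeks from the initial imaging showing progression", and "Clinically stable patients will continue treatment in the interim before this scan". Such a patient is classed as progressed only if the repeat scan agrees. With clinical deterioration, progression counts without a second scan. Section 13.3 also closes the best-response window at progression, and section 6.7 lists confirmed radiographic progression among the mandatory reasons to stop trial treatment.

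**The concern.** A purely relative threshold shrinks with the lesion. In very small disease it falls to a few millimetres, where a difference between two readings may be measurement error and not growth.

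False progression would date PFS too early. It could also turn stable disease into progression as best response, and close the window in which a later response counts. Section 7.6 makes progression the entry to a second biopsy and second treatment, so a falsely progressed patient could also enter the population of secondary objective 3. The problem is confined to patients with a small baseline sum.

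**Working it through.** The plan gives no figure to reproduce here, so the check starts from the rule itself.

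**Threshold in millimetres** = 0.20 × baseline sum:
- 10 mm: 2.0 mm
- 12 mm: 2.4 mm
- 15 mm: 3.0 mm
- 20 mm: 4.0 mm
- 25 mm: 5.0 mm
- 50 mm: 10.0 mm

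**Model for false progression.** One lesion has unchanged true size m. The baseline B and each later scan X are read with independent normal error of SD s, and entry requires B > 10 mm. Progression is scored when X ≥ 1.2 B. The documents give no s, so 0.5 to 2.0 mm is an assumed range.

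**Hand check for one scan.** X − 1.2 B has mean −0.2 m and SD s × √(1 + 1.44) = 1.562 s. For m = 15 and s = 1, P = Φ(−3.0/1.562) = Φ(−1.92) = 2.7%, which matches the simulation. For m = 12 and s = 1, Φ(−2.4/1.562) = Φ(−1.54) = 6.2%. The entry condition removes the smallest baseline readings and brings this to 4.8%.

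**Why confirmation only partly helps.** Two later scans share the same B. The correlation between their two comparisons is 1.44/2.44 = 0.59. If they were independent, the 12 mm, 1.0 mm SD case would give 0.048² = 0.2% on both scans; the simulated figure is 1.0%.

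**Simulation, no true change, 1,000,000 draws per row:**

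| True lesion | Error SD (mm) | First scan only | First, confirmed at second | Any consecutive pair in seven scans |
|---|---|---|---|---|
| 12 mm | 0.5 | 0.1% | 0.01% | 0.04% |
| 12 mm | 1.0 | 4.8% | 1.0% | 4.3% |
| 12 mm | 1.5 | 9.9% | 2.5% | 10.1% |
| 12 mm | 2.0 | 13.0% | 3.6% | 14.0% |
| 15 mm | 0.5 | 0.01% | 0.0% | 0.0% |
| 15 mm | 1.0 | 2.7% | 0.7% | 2.3% |
| 15 mm | 1.5 | 10.0% | 3.8% | 10.8% |
| 15 mm | 2.0 | 16.3% | 7.2% | 19.0% |

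The first-scan column applies directly only where deterioration removes the need for confirmation. The seven-scan column needs about 7 × 8 = 56 weeks of imaging with the lesion unchanged.

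**With an added 5 mm minimum** (SD 1.0 to 2.0 mm), the seven-scan figures fall to 0 to 0.2% at 12 mm and 0 to 2.7% at 15 mm. A minimum of F mm matters only when 0.20 × sum < F. At F = 5 that is a sum below 25 mm.

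**Patients affected.** The documents do not give the share with sums below 25 mm. If it is 10% to 25%, that is 4 to 10 of 40. For SD 1.0 to 2.0 mm:
- First scan confirmed at second: 4 × 0.7% = 0.03 to 10 × 7.2% = 0.7 patients.
- Any pair in seven: 4 × 2.3% = 0.1 to 10 × 19% = 1.9 patients.

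**The case against.** The strongest reply is that section 13.3 already deals with this. A reader might infer from Table 4 alone that a single 2 to 3 mm misreading makes a patient progressive or takes the patient off treatment. The documents do not support that for a clinically stable patient, because both the classification in section 13.3 and the stopping reason in section 6.7 need confirmation. The exception requires clinical deterioration, and such patients are unlikely to be pure measurement-error cases. This part of the reply stands. What remains is the shared baseline reading, which a repeat scan cannot correct.

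A second reply concerns endpoints. Best response is the best recorded before progression, so stable disease at the first scan is not erased by later false progression. Taking disease control as stable disease or better, the relevant figure in stable patients is the first-scan-confirmed column, not the seven-scan one. That is right. A reader might also infer bias in the primary response rate. The simulation contains no true change and so no responders. Losing a response would need confirmed false progression followed by real shrinkage, and nothing here quantifies that.

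Third, every frequency rests on an assumed reading error and an assumed share of small sums. Section 13.1 also favours larger, reproducibly measurable lesions and up to five targets, which works against the worst case. This stands as a limit on size.

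Fourth, section 13.2 cites RECIST 1.1, so Table 4 may be only a summary of it. But Tables 4 to 6 are what section 13.2 points to for scoring, and Table 4 states a single size condition. If more is intended, it needs to be written there.

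**Conclusion.** The gap is real, and its expected effect is small. Table 4 has no absolute minimum, and for a single lesion of 10 to 15 mm a change of 2 to 3 mm meets the progression criterion on that scan. Confirmation reduces false progression but does not remove it. The confirmed first-scan risk is about 1.0% to 3.5% at 12 mm and 0.7% to 7.2% at 15 mm for assumed SDs of 1.0 to 2.0 mm. Over seven scans it is about 4% to 14% and 2% to 19%. It is near zero at 0.5 mm.

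In the whole trial this is from well under 1 to about 2 patients, if 4 to 10 of 40 have small sums. PFS is the endpoint most exposed; the plan does not say whether it is dated at the first or the confirmatory scan. Disease control is affected less, and any effect on objective response is indirect and unquantified. A cheap scoring clarification is justified; a claim that the primary result is compromised is not.

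**What to change.** In Table 4, for scoring best overall response and PFS, require an absolute minimum increase in the sum in addition to the 20%. Leave progression by new lesions and by non-target lesions as written. A value of 5 mm would serve as an example. It is a proposal of this review, not a figure from the documents, and it changes nothing at baseline sums of 25 mm or more.

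The sponsor should also reconcile Table 4 with the RECIST 1.1 criteria it cites, and with the use of progression in sections 6.7 and 13.3. Otherwise endpoint scoring and treatment decisions could rest on two different definitions without the plan saying so.

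The cost is one clause in Table 4 plus that reconciliation. The downside is that true growth below the minimum in very small disease is scored one or more scans later: 5 mm is a 50% increase at 10 mm and 33% at 15 mm.

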2. PFS
3. OS
4. Adverse events

Exploratory Biomarker Studies:

- A. Immune gene expression and immune co-signaling molecule expression by IHC and immune cell populations over time;
- B. Co-signaling molecule expression by IHC and correlate with gene expression by RNAseq as well as the predictive value of co-signaling molecule expression by IHC and the efficacy of the combination selected.
- C. Evaluation of immune cell populations in the peripheral blood at baseline and over time.
- D. Evaluation of saliva and stool microbiome to determine if any correlation with efficacy of the combination selected

Study Design:

This is a phase II trial. Patients who meet eligibility criteria will have tumor tissue obtained (core or excisional/incisional; a FNA is not adequate) for gene expression of LAG3 and CTLA4 per OmniSeq Immune Report Card to determine which drug (either Relatlimab or Ipilimumab) will be added to Nivolumab for treatment. The patient will then receive the prescribed therapy continuously for up to 24 cycles (1 cycle = 4 weeks of treatment) with repeat imaging prior to every 3rd cycle until progression of disease. Response, evaluated by RECIST 1.1, with modifications to allow for continued therapy until progressive disease is confirmed if the patient is clinically stable, will be used in the trial. If the patient has confirmed progression and meets eligibility criteria to obtain a second biopsy, he or she will continue on trial and undergo a repeat biopsy for gene expression of LAG3 and CTLA4 per OmniSeq Immune Report Card to select another agent to add to Nivolumab. The patient will then be treated with this new combination continuously, with repeat imaging prior to every 3rd cycle as per initial treatment, until progression of disease. (see Schema A).

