6.7 SUBJECT WITHDRAWAL/DISCONTINUATION CRITERIA

Subjects may withdraw consent at any time for any reason or be dropped from the trial at the discretion of the

investigator should any untoward effect occur. In addition, a subject may be withdrawn by the Investigator if enrollment into the trial is inappropriate, the trial plan is violated, or for administrative and/or other safety reasons.

A subject must be discontinued from the trial treatment for any of the following reasons:

- The subject withdraws consent.
- Confirmed radiographic disease progression. See Section 13.0
- Unacceptable adverse events as described in Section 12.0
- Intercurrent illness that prevents further administration of treatment
- Investigator's decision to withdraw the subject
- The subject has a confirmed positive serum pregnancy test
- Noncompliance with trial treatment or procedure requirements
- The subject is lost to follow-up
- Administrative reasons

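### Table 4 measures target-lesion progression from the baseline sum, so patients whose tumours shrink must regrow far more than 20% before progression is called

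*Combined protocol and SAP*

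**What the plan says.** Table 4 (Section 13.2) defines target-lesion PD as "At least a 20% increase in the sum of the diameters of target lesions compared to baseline sum of target lesions", or any new lesion. Table 5 adds, for non-target disease, "Appearance of one or more new lesions and/or unequivocal progression of existing non-target lesions". Section 13.1 also names baseline as a reference, but for shrinkage: "The baseline sum diameters will be used as reference to further characterize any objective tumor regression in the measurable dimension of the disease". No part of Section 13 mentions the smallest sum recorded on study.

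Section 13.2 says response is based on RECIST 1.1 and points to Tables 4 to 6. The only modification announced (synopsis, Study Design; repeated in 4.1) is "with modifications to allow for continued therapy until progressive disease is confirmed if the patient is clinically stable". In clinically stable patients, Section 13.3 requires that progression "will be confirmed with a repeat CT scan at least 4 weeks from the initial imaging showing progression".

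Three things depend on this definition:

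- **Treatment stop.** Section 6.7 lists "Confirmed radiographic disease progression. See Section 13.0" among the mandatory reasons.
- **Second biopsy and second treatment.** Section 4.1 makes these follow confirmed progression; 7.6 gives the conditions.
- **PFS.** It appears in all three secondary objectives and is analysed by Cox regression under 15.2.2 and 15.2.3. The documents give no separate definition of a PFS event.

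**The concern.** A baseline reference suits a measure of shrinkage. Used for progression, it gives a patient credit for earlier shrinkage: the better the initial response, the more regrowth is tolerated before progression is declared. In this trial that affects more than a reported date. A patient whose tumour is clearly regrowing can stay on the first combination because the protocol criterion is not met, and the biopsy that could lead to the other combination waits. Entry to the second treatment requires the patient still to meet eligibility (7.6), including ECOG 0-1 (5.1), so waiting could cost some patients that option; how many is unknown.

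For PFS, the postponement falls only on patients who shrink. Simulations 1 and 3 in Table 10 assume more response in the favourable-score group, and the OmniSeq response score is a covariate in the PFS model. The effect therefore need not be even across the groups being described.

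**Working it through.** **Inputs.** PD threshold: 1.20 × baseline sum (Table 4). PR threshold: 0.70 × baseline sum (Table 4). Comparator, which is the rule proposed here and is not printed in the documents: 1.20 × smallest sum so far, baseline included. The documents give no figure of their own to reproduce.

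**Regrowth required.** If the sum falls by a fraction s, the smallest sum is (1 − s) × baseline. Regrowth from that point to Table 4 PD is 1.20/(1 − s) − 1. With a baseline of 100 mm:

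| Fall | Smallest sum (mm) | PD in Table 4 (mm) | PD at 20% over smallest (mm) | Regrowth needed in Table 4 |
|---|---|---|---|---|
| 10% | 90 | 120 | 108 | 33.3% |
| 20% | 80 | 120 | 96 | 50.0% |
| 30% | 70 | 120 | 84 | 71.4% |
| 40% | 60 | 120 | 72 | 100.0% |
| 50% | 50 | 120 | 60 | 140.0% |
| 60% | 40 | 120 | 48 | 200.0% |
| 70% | 30 | 120 | 36 | 300.0% |

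Any sum from the fourth column up to just under 120 mm is progression by the comparator but not by Table 4. After a 50% fall that band is 60 to under 120 mm.

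**Direction.** The smallest sum never exceeds baseline, so 1.2 × smallest ≤ 1.2 × baseline. Any scan that meets Table 4 also meets the comparator, so Table 4 is never earlier. The two rules agree when there was no shrinkage, or when growth crosses both thresholds between consecutive scans.

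**Primary endpoint.** The PR threshold is the same under both rules. However, best response is "The best overall response is the best response recorded from the start of the treatment until disease progression/recurrence", so a later PD date lengthens the window in which a response can count. Take a patient who goes 100, 80, 96 mm, with the regrowth confirmed on a second scan. The comparator closes the window; Table 4 leaves it open. To become a responder the sum must then fall to 70 mm or less, a fall of 1 − 70/96 = 27.1%, and 13.2 asks for that response to be confirmed as well. For other patients not yet in PR, the fall needed is 1 − 70/108 = 35.2% after a smallest sum of 90 mm, and about 1 − 70/84 = 16.7% after one just above 70 mm. Such a reversal after confirmed regrowth should be rare.

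**Patients exposed.** Table 10 assumes overall response of 0.100 to 0.243: 40 × 0.100 = 4.0 and 40 × 0.243 = 9.7, so about 4 to 10 responders. Patients who shrink by less than 30% add an unstated number. Only those who progress first through target lesions are affected.

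**The case against.** The strongest reply is that RECIST 1.1 governs, not Table 4. The primary endpoint is stated by RECIST 1.1, and the confirmation paragraph in 13.3 also speaks of progression by those criteria. On that view Table 4 is a loose summary and assessors would apply the published rule. This does not settle the matter. Section 13.2 offers Tables 4 to 6 as the form in which the criteria are used, 6.7 sends the reader to Section 13, and no change to the PD reference is announced. If baseline is intended, the consequence above follows. If another reference is intended, Table 4 contradicts it and two assessors could code the same scan differently. The row needs correcting either way, and the argument does not depend on the RECIST text, which the documents do not reproduce.

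Several limits do stand:

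- The link to PFS is an inference: with no separate event definition, its progression component can only rest on Section 13.
- New-lesion, non-target and death events do not move.
- Section 6.7 also allows stopping on the investigator's "decision to withdraw the subject", so the stop is later only where the progression criterion triggers it.
- The efficacy and toxicity pausing rules in 15.3 do not use PFS.
- The direction holds against a plain 20% rule; a minimum absolute increase can reverse it at small sums.

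**Conclusion.** The concern holds. As written, target-lesion progression after a 30% to 50% fall requires 71% to 140% regrowth from the smallest sum, against 20% if that sum were the reference. For patients who shrink and progress first through target lesions, the PFS event, the criterion-driven stop and the second-biopsy step are later or unchanged.

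This rests on applying Table 4 literally and on PFS taking its progression events from Section 13. The documents contain no tumour-growth data, so no delay in weeks and no change in median PFS is claimed; for an individual the delay can be zero. No effect on DCR is claimed either, since the documents set no minimum duration for it. The point is worth correcting because it touches treatment decisions and a secondary endpoint; it does not undermine the primary analysis.

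**What to change.** In Table 4, define target-lesion PD as at least a 20% increase over the smallest sum recorded on study, baseline included, and state that PFS uses this definition.

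A minimum absolute increase is optional but sensible, since 20% of a 20 mm sum is only 4 mm. Taking 5 mm as an assumed example, the amended rule would be later than Table 4 only if smallest + 5 > 1.2 × baseline. Because the smallest sum cannot exceed baseline, that needs a baseline sum under 25 mm and slight shrinkage; at a 20 mm baseline, a smallest sum above 24 − 5 = 19 mm.

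The cost is wording: the sums are already measured at each scan. The price is shorter PFS and an earlier move off the first combination for some patients who shrink.

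A separate wording correction, which carries no weight in the conclusion, can go into the same amendment. The calendar footnotes in 7.1 to 7.3 set imaging every 8 weeks, before odd cycles. The synopsis, 4.1, 7.4 and 7.5 tie it to every third cycle. With scan week = 4 × (cycle − 1), the first gives weeks 8, 16, 24 and so on to 88 (11 scans); the second, read literally, gives weeks 8, 20, 32 and so on to 92 (8 scans). Use the calendar schedule throughout.
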